A number of preliminary studies conducted by our group set the stage for this proposal(1). We have extensive experience performing environmental monitoring within Baltimore city and have found that the city has high levels of biologically active indoor PM. In our prior cohort study of 150 asthmatic children, the mean (\pm SD) indoor PM concentration for PM_{2.5-10} (coarse) was $17.4 \pm 21.1 \mu\text{g}/\text{m}^3$ and for PM_{2.5} (fine) was $40.3 \pm 35.4 \mu\text{g}/\text{m}^3$, both of which were significantly higher than the average ambient measurements made over the same time period ($10.3 \pm 21.0 \mu\text{g}/\text{m}^3$ and $12.4 \pm 6.2 \mu\text{g}/\text{m}^3$; $p < 0.01$ for both comparisons). Eighty-five percent of homes had indoor levels of PM_{2.5} exceeding the EPA limit for ambient pollution (2, 14). In addition, we found that this indoor pollution is associated with increased asthma morbidity. Specifically, each $10 \mu\text{g}/\text{m}^3$ increase in PM_{2.5-10} was associated with increases of 8% in the number of days of symptoms

[figure not shown]

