Bronchoscopy: Women of childbearing age will have a repeat pregnancy test (one is already performed in the parent study) during the first month of the study to ensure eligibility as pregnant subjects would be excluded from the study). All bronchoscopies will be performed at the Johns Hopkins Hospital Endoscopy Suite, and will be consented again for the bronchoscopy on the appropriate Johns Hopkins Endoscopy Procedure consent form. Participants who meet safety criteria (including $FEV_1 > 60\%$ predicted) will fast at least 8 hours prior to the procedure and conscious sedation will be administered in accordance to Conscious Sedation Guidelines using intravenous anxiolytics. All participants will have

peripheral blood drawn and nasal rinse prior to bronchoscopy. Subjects will undergo a research fiberoptic bronchoscopy procedure with BAL fluid collected following instillation of room temperature saline in the lung. BAL and blood will be processed for the measurement of cell count and inflammatory mediators. Weekly telephone calls and home visits will occur throughout the study as needed to trouble-shoot and perform quality checks for the study.

At the completion of the first month, the subjects will enter a wash out period of at least 1 month, during which there are no interventions or assessments made. After the wash out period, the subjects will then cross over with regard to the air cleaner-sham cleaner intervention and receive the opposite intervention. During the last month of the study period, all study procedures from the 1st month are repeated. The study is concluded after the completion of the repeat bronchoscopy.

Subjects and study staff will be blinded to whether a true or sham air cleaner is randomly assigned to each home. This blinding is to reduce bias on the part of researchers and participants. Due to the crossover design, each participant serves as his/her own control. Since all participants receive the true air cleaner for one month of the study, they are not deprived of any potential benefits of the air cleaner.

1. Inclusion/Exclusion Criteria

Inclusion Criteria:

1. Age 18-50 years of age
2. Non-smoker (<100 cigarettes in lifetime)
3. Physician diagnosis of asthma
4. Symptoms of asthma and/or reliever medication use in the past 6 months
5. Living in the current residence >= 6 months within Baltimore

Exclusion Criteria:

1. Current diagnosis of another major pulmonary disease, other significant morbidity

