2. Pregnancy (as defined by a positive urine pregnancy test at screening of all women of child-bearing potential)
3. Planning to relocate residence or activity that necessitates travel away from home for prolonged period of time during the study period
4. Current use of an air cleaner in the home

2. Study Statistics

A. Primary outcome variable

The change in concentration of fine and coarse particulate matter (PM_{2.5} and PM_{2.5-10}) with the intervention of an air cleaner, compared to sham air cleaner.

B. Secondary outcome variables

1. Asthma control will be compared between the intervention and sham groups. This will include evaluation of changes in respiratory symptoms from self-reported diaries, asthma morbidity and asthma-related quality of life from questionnaires.

2. In addition, we will assess the effects of the intervention compared to the sham on other markers of asthma health. This includes lung function as measured by spirometry, and biomarkers of inflammation as measured in the blood and the lower airways via bronchoscopy.

3. Finally, we will assess the effects of the intervention compared to the sham on the indoor air nicotine concentration.

C. Statistical plan including sample size justification and interim data analysis.

We aimed to enroll 40 participants in this crossover design in order to detect with 80% power (and an alpha of 0.05) a 40% difference in PM concentrations between groups, accounting for an ultimate drop out/loss to follow up rate of approximately 10-15%. The estimate in sample size was based on a prior study from Butz et al. (18), which showed that a sample size of 77 participants was adequate to detect a 44% difference in PM concentrations between the intervention and control groups. [Note that over the course of the study, the planned sample size of 40 was not attained due to difficulties with recruitment. Only patients in the parent observational study willing to undergo bronchoscopies were recruited, resulting in a total of only 23 patients followed, with 2 lost to follow-up by the end of the study.]

A descriptive analysis will be performed with calculation of means, standard deviations, and medians for continuous variables and proportions for categorical variables. Bivariate analyses to assess differences before and after the intervention in each group will be conducted using t-tests or the Wilcoxon rank-sum test for continuous variables and χ^2 or Fisher's exact test for categorical variables.

Citations:

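### The only precision statement (80% power for a 40% PM difference) belongs to the planned 40 participants; it is not updated for the 23 followed, and no cleaner-minus-sham estimate with a confidence interval is planned

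*Combined protocol and SAP*

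**What the plan says.** All statistical text is in 2. Study Statistics of the combined protocol and SAP.

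- **Planned size (section C).** The crossover was to enrol 40 people "in order to detect with 80% power (and an alpha of 0.05) a 40% difference in PM concentrations between groups". The same sentence allows for a loss of about 10-15%. The stated basis is a prior study in which 77 participants were adequate for a 44% PM difference between intervention and control.
- **Achieved size (section C, bracketed note).** The planned 40 was not reached because of recruitment difficulties, "resulting in a total of only 23 patients followed, with 2 lost to follow-up by the end of the study".
- **Primary outcome (section A).** "The change in concentration of fine and coarse particulate matter" with the air cleaner, compared with sham. Two fractions are named, PM2.5 and PM2.5-10.
- **Design (Study Procedures).** "Due to the crossover design, each participant serves as his/her own control".
- **Analysis (section C).** Means, standard deviations, medians and proportions, and then: "Bivariate analyses to assess differences before and after the intervention in each group will be conducted using t-tests or the Wilcoxon rank-sum test". Those tests are meant for the continuous outcomes; categorical ones get chi-square or Fisher's exact tests.

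The document nowhere restates power or a detectable difference for the achieved number, and nowhere mentions a confidence interval.

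**The concern.** The note tells the reader that fewer people were studied, but not what this does to the primary comparison. The 80%/40% pair stays as the document's only statement of precision, and it describes a sample that was not obtained.

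The analysis paragraph does not fill the gap. The primary question is cleaner against sham within the same home. The tests described are before/after comparisons inside each group, and the rank-sum test is a test for independent samples. No estimator of the cleaner-sham contrast and no interval for it is specified.

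If fine or coarse PM gave a non-significant result, the plan as written would give no basis for deciding whether a 40% reduction had been ruled out or merely missed.

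**Working it through.** **Inputs from section C:** 40 enrolled; 80% power; alpha 0.05; 40% difference; 10-15% loss; 23 followed, 2 lost; prior study of 77 for 44%.

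**Not given:** SD of the within-person difference, within-home correlation, analysis scale, sidedness, and the PM fraction to which the 40% refers. I assume a two-sided test.

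**Step 1. Try to reproduce the 40.** The dropout step is consistent: 34/0.85 = 40 and 36/0.90 = 40. The 34-36 itself cannot be derived, because n = (SDdiff × (z0.975 + z0.80) / delta)² needs an SDdiff that is not stated.

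The 77/44% basis can be scaled only by assuming that the prior study had two parallel groups and 80% power:
- Arithmetic scale: 77 × (0.44/0.40)² = 93.2.
- Log scale: 77 × (ln 0.56 / ln 0.60)² = 99.2.
- A crossover needs n = (1 − rho) × N/2 pairs, so rho = 1 − 2n/N. For n = 34 and 36 this is 0.27 and 0.23 (arithmetic), or 0.32 and 0.27 (log).

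So 40 is attainable with a within-person correlation of about 0.23-0.32, but no such value is stated. The planned 80% is neither confirmed nor refuted.

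**Step 2. Achieved pairs.** 23 − 2 = 21, if neither lost participant contributes a PM pair. The 21 is derived, not printed.

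**Step 3. Rescale power.** Take 80% at 34-36 pairs as given and solve for the standardised paired difference d (noncentral t, n − 1 df). Then apply the same d to 21 pairs.

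| Pairs at which 80% is assumed | d | Power at 21 | Power at 23 |
|---|---|---|---|
| 34 | 0.495 | 57.9% | 62.2% |
| 36 | 0.480 | 55.3% | 59.6% |
| 40 (no loss allowance) | 0.454 | 50.9% | 54.9% |

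The central range is 55-58%, and the outer range 51-62%. Variants of the central range at 21:
- n − 2 df (period term): 55-58%.
- Unpaired t-test at both sizes: 56-59%.
- One-sided alpha 0.05 (normal approximation): 60-62%.

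**Step 4. Difference detectable with 80% power at 21 pairs.** The d needed at 21 pairs is 0.643.
- Arithmetic: 0.40 × 0.643/0.495 = 0.52, and 0.40 × 0.643/0.480 = 0.54. That is 52-54%.
- Log: 40% corresponds to −ln 0.60 = 0.511. Then 1 − exp(−0.511 × 0.643/0.495) = 0.48, and with 0.480 it is 0.50. That is 48-50%.

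**Step 5. Implied 95% CI half-width (arithmetic scale).** SDdiff = 0.40/0.495 = 0.808 to 0.40/0.480 = 0.833.
- At 21 pairs: 2.086 × 0.808/√21 = 0.37, to 2.086 × 0.833/√21 = 0.38. That is 37-38 percentage points.
- At the planned 34 pairs: 2.035 × 0.808/√34 = 0.28. That is 28 points.

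Under this calibration an estimate near zero would have an interval that excludes a 40% reduction, whereas an estimate of 35% would have an interval that includes both zero and 40%. Both results are non-significant, but they mean different things, and only the interval separates them.

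**The case against.** **The shortfall is disclosed.** This stands. The 80% is worded as an aim, and the note reports the count and the reason. There is no arithmetic error and nothing is concealed. What is missing is the consequence for the primary contrast.

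**Rescaled power after the trial adds little once a CI is reported.** This largely stands, and it is why the estimate and interval come first in the fix. The rescaling keeps the plan's own 40% target and changes only n, so it is not power computed from the observed effect. It serves to mark which sample the printed 80% belongs to.

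**The contrast is already planned.** In part. The primary objective and section A name cleaner against sham, and Study Procedures makes each participant the control. The comparison is therefore intended; its estimator and interval are unspecified. Nothing prevents a CI from being reported.

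**The variance inputs may be in the cited 77-participant study.** Possibly. The supportable statement is that this document does not carry them over.

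**A stronger reading is tempting: that the trial had only about 55% power.** The documents do not support it. The figure depends on an 80% that cannot be checked, and true power may be higher or lower and may differ between fractions. The PM standard deviations in Background ("In our prior cohort study of 150 asthmatic children") do not settle it: they describe variation between children's homes and come with no within-home correlation.

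**Conclusion.** The point holds as an omission in section C. The printed 80%/40% target applied to 34-36 completers and is not updated for the achieved size. The primary cleaner-sham contrast has no specified within-person estimate or CI for either PM fraction.

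The size of the loss is known only conditionally. If 80% held at 34-36 pairs, with a paired t-test and two-sided alpha 0.05, 21 pairs give about 55-58% power for a 40% difference. Power of 80% is then reached at about 52-54% (arithmetic) or 48-50% (log). Calibrating at 40, or counting all 23 as pairs, widens these to 51-62% power, and to detectable differences of 49-57% (arithmetic) or 47-51% (log).

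A reader might also infer that a non-significant result could never count against a 40% reduction at this sample size. That is wrong: a CI that excludes 40% is evidence against it, whatever the p-value.

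Confidence is high in the omission and the conditional arithmetic. No claim is made about the trial's true power.

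**What to change.** 1. **Primary analysis (section C).** For each of PM2.5 and PM2.5-10, specify the within-person cleaner-minus-sham effect with its 95% CI (a ratio if PM is log-transformed), from a paired or period-adjusted crossover analysis. State that a non-significant result will be interpreted by whether the CI includes a 40% reduction.
2. **After the recruitment note.** Add, keeping only the scale to be analysed: *The target of 80% power for a 40% difference applied to 34-36 completers. If it held there (paired t-test, two-sided alpha 0.05), 21 pairs (23 followed, 2 lost, assuming neither gives a PM pair) have about 55-58% power for a 40% difference, and 80% power for a difference of about 52-54% (arithmetic scale) or 48-50% (log scale). This is a conditional rescaling, not a verified power for fine or coarse PM.*
3. **Basis of the original size.** State the SD or within-home correlation, the scale and the sidedness taken from the 77-participant study for each fraction, or say that none were carried over.

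Cost: a less favourable stated figure and a little more analysis work. No extra participants, visits or measurements.

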In the parent study, 100 adult subjects will be studied longitudinally during a 1-week period at baseline and again at 3 months, during which environmental monitoring of indoor air quality, as well as health assessments (respiratory symptoms, lung function and serum markers) will be conducted. As part of this initial study, we aim to further characterize the inflammatory and oxidative stress pathways that have been implicated in the airway's response to PM in the published literature. To this end, markers in the blood, will be analyzed and linked to changes in indoor particulate matter. Subsequently, a subset of 40 subjects from this cohort that meet safety criteria will then be randomized to having one of two interventions—HEPA air cleaners or sham air cleaners—placed in the home for 1 month's duration. After this month, the true or sham air cleaner will be removed from the home, and no machines will be present in the home for at least another month (washout period). In the final month of this study, the two intervention arms will be crossed over in a blinded fashion, and true/sham air cleaners will be placed in the home again for 1 month. During the first and third months, homes will undergo continuous environmental monitoring and participants will undergo personal environmental monitoring, along with simultaneous health assessments that include questionnaires, diaries, lung function testing, and blood testing. In addition, during the last week of each month with the intervention, participants will undergo bronchoscopy, during which we will obtain airway samples in order to compare lower airway response to the interventions.

In summary, more evidence is needed to understand the local pulmonary and systemic mechanisms that contribute to the burden of asthma in susceptible populations such as urban dwellers exposed to high levels of indoor pollution. Furthermore, by examining the potential alleviating effect of actively reducing chronic exposure to air pollution in the indoor environment, we aim to strengthen the causal relationship between PM and worsening asthma. Such evidence has the promise to lay the groundwork for future clinical recommendations and public policies for environmental control practices.

Objectives (include all primary and secondary objectives)

Primary Objective:

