Eligible participants for this protocol will be recruited from the community and health care facilities. All study procedures will be performed as part of this research proposal, with none of the investigations part of routine care. However, clinically significant study results will be shared with participants as needed.

Over the course of 3-5 years, 40 participants that meet criteria will be recruited from the parent study (INHALE 1) which occurs over a 3 month period, and enrolled for an additional months of investigations (i.e. this study will pick up immediately after the parent study leaves off). Informed consent will be obtained at the beginning of the parent study, and hereafter, the participant will be enrolled in both INHALE 1 and INHALE 2 studies, though study procedures for Inhale 2 will not commence until the study period of INHALE 1 is completed.

The study period is broken up into 1st, 2nd, and 3rd assessment periods. During the first month, assessments of each participant's indoor air quality will be accomplished by environmental monitoring of air pollution (PM, nicotine) inside the home. During this month, either true or sham air cleaners will be placed for the entire duration of the month (see figure 1). To measure the air cleaner use compliance, air cleaners will be outfitted with a HOBO data logger, Onset Corporation (Bourne, MA) that has been exempted by Clinical Engineering. Participants will be blindly randomized into receiving one or the other during this time. During the last week of the month, health assessments will be conducted, which include in-home health questionnaires, symptom-, and activity- diaries/recalls, blood, and handheld spirometry. Participants will also be asked to wear a light backpack with air monitoring devices during the course of the day during the last week in order to measure their exposures to pollutants. Finally, at the end of the month, participants will be asked to report to the Johns Hopkins outpatient endoscopy suite for bronchoscopy, during which airway sampling will occur under conscious sedation.

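### The only planned test is before versus after within each group, not cleaner versus sham, and its rank-sum option ignores the crossover pairing

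*Combined protocol and SAP*

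**What the plan says.** Study Statistics, A. Primary outcome variable, defines the outcome as the change in fine and coarse PM "with the intervention of an air cleaner, compared to sham air cleaner". The secondary outcomes in section B are also cleaner versus sham. Study Procedures states the design principle: "Due to the crossover design, each participant serves as his/her own control".

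Section C (Statistical plan) has one sentence that names hypothesis tests: "Bivariate analyses to assess differences before and after the intervention in each group will be conducted using t-tests or the Wilcoxon rank-sum test". Those tests are meant for continuous outcomes; categorical ones get chi-square or Fisher's exact. It does not say whether the t-tests are paired. It gives no test, model or interval for cleaner minus sham.

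On the timing of measurements:
- Abstract: "During the first and third months, homes will undergo continuous environmental monitoring".
- Study Procedures, first month: "either true or sham air cleaners will be placed for the entire duration of the month".
- Study Procedures, washout: a period "during which there are no interventions or assessments made".
- Study Procedures, last month: "all study procedures from the 1st month are repeated".
- Abstract, parent study: "100 adult subjects will be studied longitudinally during a 1-week period at baseline and again at 3 months".

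Section C sizes the trial for a 40% PM difference and records that 23 participants were followed and 2 were lost.

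**The concern.** The sentence can be read in two ways, and neither gives a sound primary analysis. The two harms are alternatives and should not be added together.

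**Literal reading.** Separate before/after tests in the cleaner and sham conditions do not estimate or test the difference between them. One can reach significance and the other not when the cleaner does nothing, particularly if PM drifts for reasons shared by both conditions. The *before* value is also undefined. A device is in place throughout each monitored month and the washout has no assessments, so the only device-free readings described are the parent study's one-week readings. The second period has none of its own.

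**Loose reading.** If cleaner versus sham was meant, rank-sum is an independent-samples test while each home supplies both values. With positive within-home correlation this makes the test conservative and wastes power, the main thing a crossover with 21 completers has to offer.

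Under either reading no interval is planned, so the data could yield a percent difference but no statement of how well it distinguishes a 40% reduction from a much smaller one.

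**Working it through.** **The plan's own figure.** The planned 40 can be neither confirmed nor refuted, because the SD of the paired difference, the within-home correlation, the scale and the sidedness are not given. As a guide, take the fine PM SD on the raw scale, two-sided: n per parallel arm = 2 × [35.4 × (1.96 + 0.84)/16.1]² ≈ 76. Crossover pairs = (1 − ρ) × 76, which is 38 at ρ = 0.5, or 43–45 after 10–15% dropout. So 40 is plausible only if the analysis is paired and ρ is about 0.52–0.55.

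**Inputs.**
- Completers: 23 − 2 = 21 (section C).
- Background, child cohort: fine 40.3 (SD 35.4), coarse 17.4 (SD 21.1) µg/m³. Adult month-long averages may differ.
- True effect 40%: 0.4 × 40.3 = 16.1 and 0.4 × 17.4 = 7.0 µg/m³.
- Shape assumed lognormal or gamma. CV = 0.878 and 1.213; log-SD = √ln(1 + CV²) = 0.756 and 0.951; gamma shape = 1/CV² = 1.30 and 0.68.
- Within-home correlation r is not in the documents: assumed 0 to 0.7 (Gaussian copula).

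**What pairing is worth, by hand (fine, correlation 0.5).** Under the cleaner the SD is 0.6 × 35.4 = 21.24.
- Paired SE = √[(35.4² + 21.24² − 2 × 0.5 × 35.4 × 21.24)/21] = 6.73; 16.1/6.73 = 2.39, against a critical t of 2.09 (20 df).
- Unpaired SE = √[(35.4² + 21.24²)/21] = 9.01; 16.1/9.01 = 1.79, against 2.02 (40 df).

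The same true effect clears the threshold when paired and misses it when unpaired.

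**Loose reading: simulated power (%), fine/coarse, 20,000 replicates per cell.** Exact critical values: signed-rank W ≤ 58, rank-sum U ≤ 142.

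| r | Rank-sum, lognormal | Signed-rank, lognormal | Rank-sum, gamma | Signed-rank, gamma |
|---|---|---|---|---|
| 0 | 54/37 | 48/32 | 37/20 | 37/20 |
| 0.3 | 55/36 | 62/43 | 35/15 | 49/26 |
| 0.5 | 57/33 | 77/55 | 33/12 | 62/34 |
| 0.7 | 59/31 | 93/75 | 31/9 | 83/51 |

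At r = 0.5 the t-tests give (lognormal; gamma) unpaired 48/25; 40/16 and paired 69/43; 65/35. Actual type I error at r = 0.5 is about 0.8–1.0% for rank-sum, 0.7–1.0% for unpaired t, 4.6–5.0% for signed-rank and 3.4–4.9% for paired t.

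**Literal reading: no cleaner effect.** 10,000 replicates, pairwise r = 0.5, one device-free reading per home serving both before/after tests. The common PM fall in both conditions is an assumption. The table shows the percentage of trials with exactly one condition significant, across both fractions and shapes.

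| Common fall | Rank-sum | Signed-rank |
|---|---|---|
| 0% | 1–2 | 8 |
| 20% | 4–11 | 14–26 |
| 30% | 8–26 | 23–37 |

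About half of these favour the cleaner. A direct signed-rank test of cleaner against sham errs in 4.4–4.7%.

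**Precision.** Median paired-t 95% limits at r = 0.5:
- Fine: about 3 to 28 (lognormal) or 2 to 29 (gamma) µg/m³. Divided by 40.3, that is 7–69% or 5–72%.
- Coarse: −0.5 to 13.5 or −1.3 to 14.7. Divided by 17.4, that is −3 to 78% or −7 to 84%.

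**The case against.** The strongest reply is that the cleaner-versus-sham contrast is stated repeatedly (sections A and B, and the sample size sentence), so a sensible analyst would make it, and the unqualified t-tests could be run paired. On that reading the defect is the rank-sum alternative plus an unspecified t-test, and the error is conservative: it costs power and does not create false claims. This is fair about direction, but nothing in the plan requires the paired test or assigns any test to the contrast.

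The missing *before* reading can also be disputed. Study Procedures refers to three assessment periods, and the parent study's three-month reading is a natural baseline for period 1. Figure 1 is not shown. Even so, the washout is explicitly described as free of assessments, so at best *before* is undefined, most clearly for period 2.

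The before/after error rates depend on an assumed drift. With none, rank-sum gives only 1–2%, and the 23–37% figures use a test the plan does not name. That stands, and the tables should be read accordingly. The failure to test the contrast needs no drift assumption.

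It is also true that planned means and medians allow a percent difference to be set beside 40%; what is missing is its precision. Finally, preferring signed-rank to paired t is a judgement: under gamma at r = 0.5 the paired t does slightly better (65/35 against 62/34).

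**Conclusion.** The concern holds. From the text alone, the one inferential rule either fails to test the stated primary contrast or, through its rank-sum option, discards the pairing on which the design rests.

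The size depends on r, the assumed shape and a child-cohort SD. Using signed-rank in place of rank-sum gains 7–14 power points at r = 0.3, 20–29 at 0.5 and 34–52 at 0.7, and loses 0–6 at r = 0. Coarse PM remains poorly powered at r = 0.5 even when paired (34–55% by signed-rank). The false-positive risk belongs only to the literal reading and grows with any drift shared by both conditions. The planned analysis should be corrected; the data already collected are sufficient to do so.

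**What to change.** For the primary outcome, replace the bivariate sentence with one named within-participant comparison:

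- For each of PM2.5 and PM2.5-10, a Wilcoxon signed-rank test on each participant's cleaner-minus-sham PM, with a paired t-test as sensitivity analysis. Either paired test removes the defect. Signed-rank is suggested because, across both shapes and r = 0 to 0.7, it lost at most about 3 power points to the paired t and gained up to 15.
- Report the paired difference in µg/m³ and the percent difference, each with a 95% confidence interval, and name the interval methods. For example: Hodges-Lehmann beside the signed-rank test, a paired-t interval for the mean difference, and a ratio of geometric means for the percent. The documents do not require a log-scale primary analysis.
- If before/after comparisons are kept, label them descriptive and state which reading is *before*.
- Fix the choice before treatment-level data are seen. Section C already records the end of follow-up, so label the analysis post hoc if they have been.

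**Cost.** A few SAP sentences and a re-run on existing data. If r is near 0, signed-rank gives up as much as 6 points (fine, lognormal: 48% against 54%). Under skew the Hodges-Lehmann estimate falls below the mean difference (about 12.5 against 16.1 µg/m³; fine, lognormal, r = 0.5), so report both. The paired-t interval covers slightly below nominal (92–94% at r = 0.5). Participants with only one period drop out of the paired comparison.

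### The planned analysis of this two-period crossover has no period term, so a common shift in PM between the device months can cost power and, given an unequal sequence split, distort the true/sham estimate

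*Combined protocol and SAP*

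**What the plan says.** The Study design text under Study Procedures describes a randomised two-period, two-sequence crossover. On the first device month it says: "Participants will be blindly randomized into receiving one or the other during this time". After that month "the subjects will enter a wash out period of at least 1 month", and the opposite device follows for a further month. The gap has a minimum but no maximum. The design rationale is that "Due to the crossover design, each participant serves as his/her own control".

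Section C of Study Statistics gives the sample size ("We aimed to enroll 40 participants in this crossover design") and the target, to "detect with 80% power (and an alpha of 0.05) a 40% difference in PM concentrations between groups". A bracketed note reports 23 participants followed, of whom 2 were lost. Beyond descriptive summaries, the analysis is one sentence: "Bivariate analyses to assess differences before and after the intervention in each group will be conducted using t-tests or the Wilcoxon rank-sum test", with χ² or Fisher's exact test for categorical variables. Nowhere do the documents mention a period or sequence effect, a mixed model, an adjustment for season or outdoor PM, or blocked allocation of order.

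**The concern.** Device months lasting one month and separated by at least one month start at least two months apart. PM may differ between them for reasons unrelated to the device, such as weather, heating, or behaviour under repeated monitoring. Randomising the order lets the analysis separate such a shift from the device effect, but only if period is in the model.

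This is distinct from the fact that the named tests ignore pairing. Moving to a paired t-test or signed-rank test would leave the period shift inside each within-home difference, with opposite signs in the two sequences. At stake are precision and, if the split was uneven, the size of the primary PM estimate, in a trial that ended with about half its planned number.

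**Working it through.** **The plan's own figure.** With 10–15% loss, 40 enrolled leaves 34–36 evaluable. For 80% power at two-sided 0.05 (sidedness is not stated), a paired t-test then needs a standardised effect of 0.48–0.50. A 40% reduction is −ln 0.6 = 0.511 on the log scale, so the SD of within-home log differences would have to be about 1.03–1.06. The plan gives no such SD and no correlation. The 40 can therefore be back-solved but not reproduced.

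**Inputs.**
- Completers: 23 − 2 = 21, so 11/10 is the most even split possible.
- Between-home PM, from the prior paediatric cohort in Background: fine 40.3 (SD 35.4), coarse 17.4 (SD 21.1) µg/m³.
- Log SD = √ln(1 + (SD/mean)²), assuming lognormality: fine √ln 1.772 = 0.756; coarse √ln 2.471 = 0.951.
- Assumed, because the documents give no figure: within-home correlation ρ = 0.5, so SD_diff = log SD × √(2(1 − ρ)) = 0.756 and 0.951; period shift π = 0.2 to 0.5 in log PM (a fall of 18–39%, or a rise of 22–65%).

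**Algebra.** Let δ be the log true/sham effect and π the last-month minus first-month shift. The within-home difference (true − sham) averages δ − π in the n1 homes with true first and δ + π in the n2 homes with sham first. Pooled without a period term:
- the mean is δ − π(n1 − n2)/(n1 + n2);
- the variance rises from SD_diff² by π²[1 − ((n1 − n2)/(n1 + n2))²], or about π² when the split is near even.

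A period term removes both. Its standard error is (SD_diff/2)√(1/n1 + 1/n2) on n1 + n2 − 2 degrees of freedom.

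**Bias given the split** (apparent reduction = 1 − 0.6·exp(±bias)):

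| Split | Share of shift | True 40% appears as, shift 0.2 | Shift 0.5 |
|---|---|---|---|
| 11/10 | 1/21 = 5% | 39.4–40.6% | 38.6–41.4% |
| 12/9 | 3/21 = 14% | 38.3–41.7% | 35.6–44.1% |
| 14/7 | 7/21 = 33% | 35.9–43.9% | 29.1–49.2% |

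Under simple randomisation of 21, from Binomial(21, 0.5), the sequence sizes differ by at least 3 with probability 66%, by at least 5 with 38%, and by at least 7 (14/7 or more extreme) with 19%.

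**Variance at 11/10, ρ = 0.5.** Inflation is π²/SD_diff². Fine: 0.04/0.572 = 7% to 0.25/0.572 = 44%. Coarse: 0.04/0.904 = 4% to 0.25/0.904 = 28%. Over ρ = 0.3–0.7 the ranges are 5–73% and 3–46%.

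**Power for a 40% effect at 11/10, ρ = 0.5.** The unadjusted paired t-test was simulated; the period-adjusted test uses the noncentral t on 19 df. For fine PM the noncentrality is 0.511/(0.378 × 0.437) = 3.09. Each pair shows the two directions of the shift.

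| | With period term | Unadjusted, shift 0.2 | Unadjusted, shift 0.5 |
|---|---|---|---|
| Fine | 83.5% | 80% / 83% | 67% / 76% |
| Coarse | 65% | 61% / 65% | 50% / 59% |

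With no shift, the unadjusted test has 83.7% power for fine PM, so the period term costs about 0.3 points.

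**Type I error of the unadjusted paired test**, over both shifts, both fractions and ρ = 0.3–0.7: about 5–10% at 14/7, about 5% at 13/8, and about 2–5% (conservative) at 12/9. Averaged over simple randomisation at ρ = 0.5 it is 5.0%.

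**The case against.** The strongest reply concerns size, and much of it stands.

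- **The figures describe a test that the plan does not name.** They assume a paired true-versus-sham comparison. If the two-sample tests were applied to true versus sham, the shift would add only (π²/4)/SD² to the within-arm variance: 2–11% for fine and 1–7% for coarse PM. This is fair. The power figures show what remains once pairing is repaired. Read literally, though, a before-and-after test within each group would take in the whole shift at any split, so the literal wording is no defence.
- **The shift is assumed.** Entry over 3–5 years spreads start dates across seasons, so a shift common to all homes may be small. This stands. A period term also leaves seasonal changes that differ between homes.
- **Randomised order already protects the estimate.** It does on average, so it would be wrong to say that leaving out period gives up that protection. What remains is bias given the one split that occurred.

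A reader might infer more: that the result is in fact biased, that the 66% chance of an uneven split is a 66% chance of inflated type I error, or that power falls from 84% to 67%. The documents support none of these. They report neither the split nor the allocation method, and blocking would make 14/7 unlikely. At 12/9 the test is conservative. The 67% applies only to the largest assumed shift in the less favourable direction.

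**Conclusion.** The omission is real: a two-period crossover is to be analysed with bivariate tests that contain no period, sequence or participant term, and pairing alone would not repair it. The consequence is conditional. For an assumed log shift of 0.2 and an 11/10 split, the power loss is about 0–4 points and the bias is trivial. For a shift of 0.5 it is about 6–17 points, depending on direction and PM fraction. Bias matters mainly for splits near 14/7, where a third of the shift enters the estimate. These sizes rest on assumed shifts, an assumed correlation, lognormal PM, SDs from a different cohort, and 21 completers. The point is worth acting on because the remedy costs almost nothing, not because harm has been shown.

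**What to change.** For each PM fraction, analyse log mean concentration in the two device months with a linear mixed model: fixed effects for device (true/sham) and period (first/last), and a random intercept per participant. Report the true/sham ratio with its 95% CI, and the number of participants in each sequence. Use the same model for the continuous secondary outcomes. Add calendar season, from the monitoring dates, as a sensitivity analysis, since period removes only a shift common to all homes.

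The same model repairs the lack of pairing. It also uses any device-month data from the two participants lost to follow-up; the documents do not say whether such data exist.

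Cost: revised SAP wording, one model and one degree of freedom, under 1 point of power if there is no shift. No new data are needed. The text, dated 07/31/2019, already reports final follow-up, so the change should be labelled post hoc if it is made after the data were seen.
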